## 6.1.8.3. Urine Drug Screen

Urine drug screen will be conducted at screening Day 1 and at clinic admission visit (Day -1) in order to ensure compliance with study exclusion criteria.

Drugs of abuse will include: amphetamines, barbiturates, benzodiazepines, cannabinoids, cocaine, alcohol, opiates, phencyclidine and propoxyphene.

## 6.1.8.4. Inflammatory Markers and Cytokines

Testing of inflammatory markers and cytokines values from the 2nd, 3rd and 4th cohorts (on RZL-012 treated and placebo treated subjects in each cohort) will be conducted in order to explore the mode of action at clinic admission visit (Day -1)to establish baseline values (4 mL

blood per subject). Additional cytokines testing will be conducted study visits Day 7, 14, 21 and 28.

Inflammatory and cytokines will include: CRP, Adiponectin, CD-163, Interleukin [IL]-1β, IL-4, IL-6, IL-10, IL12p70, IL-13, IL-23, Tumor necrosis factor [TNF] α, and TGFβ1.

Inflammatory and cytokines level will be measured by multiplexed ELISA kits, called Q-PlexTM. Q-Plex Arrays are able to measure the concentration of multiple proteins in each sample and to quantify cytokines levels. Blood samples (4 mL) will be centrifuged at 1200 G in 4  $^{0}$ C for 10 minutes, plasma collected in aliquots (minimum of 2 aliquots of 500  $\mu$ L each) within 20 minutes of centrifugation and flash frozen on dry ice. Processed samples will be frozen in -80  $^{0}$ C. Plasma aliquots will be analyzed by Quansys Biosciences.

#### **6.1.8.5.** Histamine

Testing of subjects' blood histamine levels will be conducted at clinic admission visit (Day -1) visit before drug injection in order to establish a baseline (4 mL blood per subject). Additional blood histamine levels will be conducted the day following drug injection ( $24h \pm 2h$  following drug injection), at study visit Day 3 and 14.

### **6.1.8.6.** Urinalysis

Urinalysis will be conducted at screening Day 1 (performed 28 through 7 days prior to baseline) in order to ensure compliance with study inclusion criteria and to allow differential diagnosis in case of urinary tract associated AE. Additional urinalysis testing will be conducted on study visit Day 14 and 28.

Urinalysis will include: Nitrite, Sodium, Potassium, Calcium, Phosphate, Protein, RBC, WBC, Blood, Glucose, Ketone bodies, Bilirubin, Urobilirubin, Urine specific gravity, Osmolarity, and pH.

### 6.1.9. ECG

Subjects' ECG will be performed at screening Day 1 (performed 28 through 7 days prior to baseline) in order to ensure compliance with study inclusion criteria. ECG is to be performed on at least a triplicate of heartbeats for all measurements and will be recorded at a speed of 25 mm/sec. Additional ECGs will be performed at  $4h \pm 30$ min,  $12h \pm 30$ min and  $24h \pm 2h$  following drug injection (Day 0-1) and on Days 14 and 28.

Computerized ECG analysis will include: Heart rate, Rhythm, PR interval, QRS axis, and QRS duration. QT interval and QTc will be calculated manually according to the Bazett formula. ECG will be recorded at a standard speed of 25 mm/sec and standard amplitude of 10 mm/mV.

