#### Baseline visit (Day 0):

- Baseline visit will be in an in-patient setting. Subjects will be interned in the study site for visit baseline till the following day.
- Pre-treatment: eligibility confirmation, randomization, vital signs, Draize score, First blood sample for pharmacokinetics will be taken.
- Treatment All injections will be administered 45 ° to the skin surface using a 1 mL Luer-lock syringe and a 30 G x 1/2" needle (the hole of the needle pointing into the fat layer). The first injection site will be at 5 cm lateral to the umbilicus lateral wall into the left or right abdominal subcutaneous fat.
- Post treatment: ECG (4h and 12h ± 30min post injection), pulse rate (1h, 2h, 4h, 8h, 12h, 24h post injection in the opposite hand of blood sampling), vital signs (2h ± 30 min post injection), Draize score (2h post injection ± 30 min), adverse events (AEs) will be recorded and pharmacokinetics.

Pharmacokinetics with cohorts 1-4—RZL-012 half-life was determined to be 5 hours in the exploratory phase 0 clinical trial (protocol RZL012-P0US-001.3), therefore blood samples will be taken after injection at the given time points: 0, 30, 60 min, 2h, 3h, 4h, 6h, 8h, 12h, 16h,24h, 30h.

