#### 1.2.1.2. Safety Pharmacology

The effect of RZL-012 on the central and peripheral nervous systems was evaluated using the Functional Observational Battery (FOB) in male Sprague Dawley rats. RZL-012 was administered subcutaneously to rats (n = 8/group) as 10 mg/rat. From the results it was

concluded that RZL-012 did not affect any of the central nervous system functions tested using functional observation battery in rats.

The effect of RZL-012 was evaluated on respiratory functions in male Sprague Dawley rat using head-out plethysmography. RZL-012 was administered subcutaneously at a fixed dose of 10 recorded to cover the entire predetermined time points; Pre-dose, 1, 2, 3, and 4 h post dose. RZL-012 did not affect any of the parameters tested hence it was concluded that RZL-012 has no effects on the respiratory system at the tested dose of 10 mg/rat.

A board-certified veterinary cardiologist conducted a qualitative and quantitative review of the electrocardiograms obtained pretest, pre-dose, 4 and 24 hours post-dose following the subcutaneous injection of 500 mg 5.0 % RZL-012 or vehicle in Domestic Yorkshire Crossbred Swine. There was no effect of the subcutaneous injection of 5.0 % RZL-012 on qualitative or quantitative ECG parameters or blood pressure.

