#### 1.2.2.1.2. Pigs

This study was conducted to evaluate the potential local and systemic toxicity as well as efficacy of the test article, RZL-012 (50 mg/mL), in domestic Yorkshire crossbred swine following

subcutaneous injection into the subcutaneous abdominal fat on Day 0. Methods and results from the extended single dose toxicity in pigs study are described in details in the Investigator's Brochure.

Assessment of toxicity was based on mortality, clinical observations, body weight, qualitative food consumption, body temperature, subcutaneous fat temperature, blood pressure; physical and electrocardiographic examinations; and anatomic and clinical pathology. Blood samples were collected and analyzed for porcine stress syndrome testing, histamine level analysis, and toxicokinetic assessment of the test article.

Administration of the test article was not associated with any mortality, clinical observations (with the exception of transient redness and swelling at injection sites), body weight or food consumption changes, effects on electrocardiographic endpoints, or changes clinical chemistry or coagulation parameters. It should be noted that three animals died during the post anesthesia recovery period. The cause of death was considered to be related to perioperative complications associated with the anesthesia and not related to RZL-012 or saline administration. These three animals were replaced on study.

A slight elevation in body temperatures was noted in males treated with the test article from Days 14-16 until Days 77-79. In addition, several animals were observed with perioperative hyperthermia and/or hypothermia. To determine if the perioperative hyperthermia and/or hypothermia was caused by Porcine Stress Syndrome all remaining animals on study were tested and determined to be normal (negative).

Administration of the test article was associated with changes in subcutaneous fat temperatures, a mild increase in neutrophils, and macroscopic and microscopic observations.

A noticeable difference in subcutaneous fat temperatures was noted between treatment groups. Beginning as early as Day 4-5, an increase in temperature was noted at all test article treated sites in both males and females. The increase in temperature was noted through Days 58-63. At study termination, subcutaneous fat temperatures at treated sites were comparable to vehicle control.

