**Table 2: Subject Information and Timeframes** 

Information	Timeframe	Follow-up Timeframe
Informed Consent Form	Signed prior to any study dedicated procedure	
Medical History and Concomitant Medications	At screening visit and at clinic admission visit (Day -1)	
Physical examination	At screening Day1 visit and at Day 28	
Vital Signs	At screening Day 1 visit and at Days 0 (pre and following injection), 1, 7, 14, 21, 28	
Pulse rate	At Day 0 (pre and following injection) and at day 1	
ECG	At screening Day 1 visit, at Day 0 (following injection) and at Days 1, 14, 28	
Anthropometric Measurements: weight, height (screening only), BMI, waist circumference, hip circumference	At screening Day 1 visit, screening Day 2, clinic admission visit (Day-1) and at Day 28	Every 28 days. On Days 56, 84, 112, 140, 168
Weight – measured at home by the subjects at morning (8-12h fast) and at bedtime	At Days 7, 14 and 21	Every week when not visiting the site
Draize Score at the Injected Site	At screening Day 1 and at Days 0 (pre- and following injection), 1, 7, 14, 21, 28	Every 28 days.
Serology assays (HBV, HCV and HIV)	At screening day1 visit	
Urine drug screen	At screening Day 1 visit and at clinic admission visit (Day -1)	
Serum chemistry	At screening Day 1, at clinic admission visit (Day -1) and at Day 1, 3, 7, 14 and 28	
Hematology	At screening Day 1, at clinic admission visit (Day -1) and at Day 1, 3, 7, 14 and 28	
Fasting Glucose	At screening Day 1	
Fasting Glucose, Insulin, Leptin, Lipid Profile and FFA	At clinic admission visit (Day -1) and at Day 28	Every 28 days. On Days 56, 84, 112, 140, 168
Urinalysis	At screening Day 1 visit and at Days 14, 28	

Information	Timeframe	Follow-up Timeframe
Cytokines and inflammatory markers— in subjects from the 2 nd , 3 rd and 4 th cohorts	At clinic admission visit (Day -1) visit and at Days 7, 14, 21 and 28	
Histamine	At clinic admission visit (Day -1), and at Day 1, 3 and 14	
Pharmacokinetics in subjects from all cohorts	At Day 0-1	
Photography of the Injected Sites	At screening Day 1 visit and at Days 1, 7, 14, 21, 28	Every 28 days. On Days 56, 84, 112, 140, 168
Thermal Imaging	At screening Day 1 visit,at clinic admission visit (Day - 1)and at Days 1, 7, 14, 21, 28	On Day 56

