- Local inflammation (minimal to moderate) with muscle degeneration, epidermal/dermal necrosis (minimal to severe) and parakeratosis (minimal). Inflammation observed at injection site was also extended to adjacent subcutaneous adipose tissue. By 56 days the inflammation was minimal, muscle degeneration was not evident and inflammation to adjacent subcutaneous adipose tissue was present.
- A slight elevation in body temperatures was noted in male pigs.
- Sinus tachycardia (in pigs), occurring at the 4 hour interval post dosing.
- In addition, other acceptable treatment to relieve drug-related AE's should be used at Investigator's discretion.

Study subjects must be informed of possible AEs that occurred in clinical studies (phase 0):

- At the injection site -local and transient: erythema, oedema, pruritus, anesthesia, pain, mass (subcutaneous scar).
- Abdominal abscess

26 May 2017 58 CONFIDENTIAL

• Transient moderate to severe elevation of the liver enzymes: Alanine aminotransferase (ALT) and Aspartate aminotransferase (AST).

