14.3.2 Other safety Assessments

Medi Stat Statistics in Medicine	DOCUMENT NUMBER: 050-BST-PLN-001	PAGE: 29 of 31
TITLE: Statistical Analysis Plan		EFFECTIVE DATE: 14/Nov/2018 REVISION NUMBER: 2.0

Table 14.3.2-1: Summary of Vital signs

Table 14.3.2-2: Changes from baseline - Vital signs

Table 14.3.2-3: Summary of Chemistry

Table 14.3.2-4: Changes from baseline – Chemistry

Table 14.3.2-5: Summary of Hematology

Table 14.3.2-6: Changes from baseline – Hematology

Table 14.3.2-7: Summary of Coagulation

Table 14.3.2-8: Changes from baseline – Coagulation

Table 14.3.2-9: Summary of Glucose

Table 14.3.2-10: Changes from baseline - Glucose

Table 14.3.2-11: Summary of Lipids

Table 14.3.2-12: Changes from baseline - Lipids

Table 14.3.2-13: Summary of Plasma

Table 14.3.2-14: Changes from baseline - Plasma

Table 14.3.2-15: Summary of Serum

Table 14.3.2-16: Changes from baseline – Serum

Table 14.3.2-17: Summary of Urinalysis

Table 14.3.2-18: Changes from baseline - Urinalysis

Table 14.3.2-19: Summary of Urinalysis - Categorical results

Table 14.3.2-20: Summary of Serology at Screening

Table 14.3.2-21: Summary of Drug Screening

Table 14.3.2-22: Summary of ECG Results

Table 14.3.2-23: Changes from baseline - Urinalysis

Table 14.3.2-24: Summary of Draize Score

Table 14.3.2-25: Summary of Physical Examination

Table 14.3.2-26: Any concomitant medications

Medi Stat Statistics in Medicine	DOCUMENT NUMBER: 050-BST-PLN-001	PAGE: 30 of 31
TITLE: Statistical Analysis Plan		EFFECTIVE DATE: 14/Nov/2018 REVISION NUMBER: 2.0

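### QTc is corrected by Bazett alone, so a rise in heart rate at the first post-dose ECG (4 h) could read as QTc prolongation; report Fridericia as the main QTc and add the missing ECG change table

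*Protocol*

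**What the plan says.** **Formula.** Protocol 6.1.9: "QT interval and QTc will be calculated manually according to the Bazett formula". The same section has heart rate read from each ECG. The SAP names no correction formula, and neither document sets a QTc category or threshold.

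**Timing.** The Day 0 procedures in the synopsis read: "Post treatment: ECG (4h and 12h ± 30min post injection), pulse rate (1h, 2h, 4h, 8h, 12h, 24h post injection". The first post-dose ECG is therefore at 4 h, with a pulse reading at the same hour. The ECG row of Protocol Table 2 reads "At screening Day 1 visit, at Day 0 (following injection) and at Days 1, 14, 28", so the only scheduled pre-dose ECG is at screening, between Day -28 and Day -7.

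**Heart-rate signal.** Among the animal findings of which subjects must be told, Protocol 7.2 lists: "Sinus tachycardia (in pigs), occurring at the 4 hour interval post dosing". It does not give the size of the rise.

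**Statements the other way.** Protocol 1.2.1.2, on swine ECGs taken pretest, pre-dose, 4 h and 24 h after dosing: "There was no effect of the subcutaneous injection of 5.0 % RZL-012 on qualitative or quantitative ECG parameters or blood pressure". In the pig toxicity study (1.2.2.1.2), the things with which the test article was not associated include "effects on electrocardiographic endpoints, or changes clinical chemistry or coagulation parameters". Protocol 1.2.4 reports no clinically significant ECG or vital-sign change in phase 0, at doses of 5 to 20 mg; the present trial starts at 40 mg.

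**Analysis.** The synopsis (Safety Analysis) promises change-from-baseline summaries for ECG, and Protocol 10.5.7 makes the safety analysis descriptive. The SAP lists "Table 14.3.2-22: Summary of ECG Results" and, directly after it, "Table 14.3.2-23: Changes from baseline - Urinalysis". The latter repeats the title of Table 14.3.2-18. No ECG change-from-baseline table is listed.

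**The concern.** Bazett divides QT by the square root of the RR interval. If QT shortens less with rate than a square-root law implies, the corrected value climbs with heart rate although nothing has happened to repolarisation. The protocol itself flags a possible heart-rate effect at 4 h, takes its first post-dose ECG then, and reports only this correction.

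ECG is one of the listed components of the safety evaluation (Protocol 6.1.17.1.1 and 10.2.4). The DSMB decides on each escalation after reviewing all safety data to Day 14 (Protocol 3.3.1), a window that contains the 4 h, 12 h, 24 h and Day 14 ECGs. A rate-driven QTc rise could therefore be in front of the DSMB at each step. Placebo would cancel a rate change common to both arms, but not one confined to active subjects, and each cohort has only two placebo subjects.

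**Working it through.** The plan states no QTc figure, so there is nothing to reproduce. The check asks how far each formula moves when heart rate changes and true QTc does not.

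**From the documents:** Bazett only (Protocol 6.1.9); first post-dose ECG at 4 h ±30 min (synopsis, Day 0, and 6.1.9); heart rate read from the ECG (6.1.9).

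**Assumed, because the documents give no values:** true QTc 400 ms; resting heart rate 65 bpm; a rise of 10 to 40 bpm; true exponent b between 0.25 and 0.50.

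**Formulas,** with RR = 60/HR in seconds:
- True relation: QT = 400 × (60/HR)^b
- Bazett: QT / (60/HR)^(1/2) = 400 × (HR/60)^(1/2 − b)
- Fridericia: QT / (60/HR)^(1/3) = 400 × (HR/60)^(1/3 − b)

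Bazett rises with heart rate for every b below 1/2. Fridericia rises for b below 1/3 and falls for b above it.

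**Worked case, b = 1/3, 65 to 85 bpm:**
- At 65 bpm: Bazett = 400 × (65/60)^(1/6) = 405.4 ms
- At 85 bpm: Bazett = 400 × (85/60)^(1/6) = 423.9 ms
- False change: +18.5 ms. Fridericia stays at 400 ms.

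**The same rise at other exponents:**

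| True exponent b | Bazett change (ms) | Fridericia change (ms) |
|---|---|---|
| 0.25 | +28.3 | +9.1 |
| 1/3 | +18.5 | 0.0 |
| 0.40 | +11.0 | −7.1 |
| 0.50 | 0.0 | −17.3 |

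**False Bazett change for other rises from 65 bpm:**
- b = 1/3: +9.8, +18.5, +26.5 and +33.7 ms for rises of 10, 20, 30 and 40 bpm.
- b = 0.25: +14.9 ms (10 bpm) to +52.0 ms (40 bpm).
- b = 0.40: +5.8 to +19.8 ms over the same rises.
- b = 0.50: zero throughout.

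**Where Fridericia stops being better.** The two errors are about equal in size when 1/2 − b = b − 1/3, that is b = 5/12, about 0.42. Below that Fridericia has the smaller error; above it Bazett does.

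**The case against.** The strongest reply is that the heart-rate signal is doubtful. Two nonclinical summaries report no ECG effect in swine, one of them with a 4 h recording. Phase 0 was clean, and tachycardia is not among the phase 0 events listed in Protocol 7.2. This stands in part: the animal evidence is inconsistent and cannot be called an established effect. It does not dispose of the point, because the highest phase 0 dose (20 mg) is half the first dose here (40 mg), and Bazett's dependence on rate does not turn on what caused the rate to change.

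Second, any single figure borrows its answer from the assumed exponent. Holding Fridericia QTc constant makes Fridericia right by construction. This stands, and is why a range is given. At b = 0.50 Bazett is exact and Fridericia is the biased one.

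Third, QTc has no threshold, the ECG summary is descriptive, and the error for a rising rate is towards caution. This stands for consequence. The direction holds only if rate rises, however. A rate lower than at screening reverses the sign: 85 to 65 bpm at b = 1/3 gives −18.5 ms.

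Fourth, having no scheduled pre-dose ECG after screening weakens QTc change under any formula. That is true and is a separate limitation. A change of formula does not cure it, but it is one more way for rate differences to enter the change from baseline.

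A reader might go further in two directions that the documents do not support:

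- **That an inflated QTc could count as a Grade 3 event and help stop a cohort.** Neither document gives QTc grade limits. Grading refers to CTCAE v4.03, which is not reproduced, and nothing shows that shifts of this size would reach Grade 3. The event would also have to be judged possibly or probably related.
- **That a QTc effect could not be separated from heart rate.** QT and heart rate are both recorded, so the two can be separated at any time. The gap is in what is planned to be reported.

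**Conclusion.** The point holds as a minor, inexpensive improvement to the ECG safety reporting. Bazett is the only correction planned, and it over-reads with rising heart rate for any true exponent below 0.5. The protocol names a possible heart-rate effect at the hour of the first post-dose ECG, while other sections of the same protocol report no ECG effect in swine.

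For an assumed rise from 65 to 85 bpm with no true QT effect, the false change runs from zero (exponent 0.50) to about +28 ms (exponent 0.25). It would be zero if human heart rate did not change. The conclusion that Bazett depends on rate needs only an exponent below 0.5; the size depends wholly on the assumed heart rates and exponent.

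The consequence is a possibly misleading QTc signal in a descriptive table and in the DSMB's review. The efficacy analysis is untouched, and no route to the intolerable-side-effect rule is shown.

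**What to change.** 1. Derive Fridericia QTc from the QT and heart rate already recorded. State in the SAP that it is the main QTc and Bazett the secondary one.
2. Add an ECG change-from-baseline table to the SAP, by treatment, cohort and time point, with both QTc values and the change in heart rate side by side. Table 14.3.2-23, which now follows the ECG summary under a duplicate urinalysis title, is the natural place. Whether it was meant for ECG cannot be told from the SAP, so the sponsor should confirm.
3. Give the DSMB the same two QTc values and heart rate at each cohort review.
4. Reconcile Protocol 7.2 with 1.2.1.2 and 1.2.2.1.2 on swine heart rate and ECG, and set the phase 0 ECG result in 1.2.4 beside them.

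The cost is one derived variable and one table, with no new ECGs, visits or subjects; it can also be done on data already collected. The drawback is that Fridericia under-corrects if the true exponent is near 0.5 (−17 ms in the worked scenario), which is the reason to report both.

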#### 6.1.10. Draize Score

Subjects' skin irritancy will be evaluated by Draize score at screening Day 1 (performed 28 through 7 days prior to baseline) in order to establish a baseline to compare following drug injection.

Additional skin irritancy evaluation to assess subject's safety will be performed at baseline visit prior to injection, and on  $2h \pm 30$ min following injection, on the following day  $24h \pm 2h$  after drug injection and on study visits Day 7, 14, 21, and 28. For the 1st and 2nd cohorts if by visit Day 56 Draize score is not 0 for erythema and edema, then subject will continue to be followed every 28 days till Draize score is 0. If Draize score is 0 for erythema and edema, then subjects of these cohorts will be followed for additional 2 months (every 28 days) by phone for adverse events. For the 3rd and 4th cohorts (or the highest dose achieved) Draize score will be assessed every 28 days during the follow-up period.

Skin irritancy observations in the injected sites and contra-lateral sites will be scored using the Draize scale for scoring skin reaction:

Erythema and eschar formation		Edema formation				
No erythema	0	No edema	0			
Very slight erythema (barely perceptible)	1	Very slight edema (barely perceptible)	1			
Well defined erythema		Slight edema (edges are well defined by definite raising)	2			
Moderate to severe erythema	3	Moderate edema (raised approximately 1mm)	3			
Severe erythema (beet redness) to slight eschar formation (injuries in depth)	4	Severe edema (raised more than 1mm extending beyond area of exposure)	4			

- Total possible erythema score = 4
- Total possible edema score = 4

## 6.1.11. Photography of the Injected Site

Documentation of the skin condition and fat reduction effect in the injected area compared to the contra-lateral non-injected area will be conducted at screening Day 1 (performed 28 through 7 days prior to baseline). Additional photography will be performed at Day 1 ( $24h \pm 2h$  following drug injection) and on study visits Day 7, 14, 21, and 28. In subjects that are followed for over 28 days, photographing will be conducted every 28 days.

Photography with a digital camera will include:

- 1. The injected area at a distance of 20 cm and in a horizontal line from the umbilicus.
- 2. The contra-lateral non-injected area at a distance of 20 cm and in a horizontal line from the umbilious.

- 3. The injected area and the contra-lateral non-injected area at a distance of 1 m and in a horizontal line from the umbilicus.
- 4. The injected area at 45 degree angle from the camera and in a horizontal line from the umbilicus
- 5. The contra-lateral non-injected area at 45 degree angle from the camera and in a horizontal line from the umbilicus.
- 6. The injected area oblique views.
- 7. The contra-lateral non-injected area oblique views.

Photography with a digital camera will be performed according to a detailed written manual.

